7.3.5.2. BAL exploratory biomarkers

The strategy for analysing and reporting BAL exploratory biomarkers will follow the same structure as the primary analysis (see Section 7.1). Details of outputs can be found in Appendix 11: List of Data Displays.

7.3.5.3. Multivariate Analysis of BAL Total Protein and Total Neutrophils

This analysis may be conducted to better understand the correlation between the endpoints and will be supported by tables and figures.

Endpoint / Variables

- Absolute BAL total protein and total neutrophil counts
- It is anticipated that biomarkers will require log-transformation in all analyses to improve model fitting. Following model fitting, back-transformation will occur and treatment comparisons at each of the sampling timepoints will be expressed as a percentage change for GSK2798745 relative to placebo.

Model Specification

- Each blood biomarker will be analysed using a repeated measures mixed model (MMRM) fitted in a Bayesian framework with all covariates having non-informative priors using PROC MCMC in SAS.
- ****analyte**** in the text below should be replaced by the specific blood biomarker in the analysis.
- The terms to be fitted in the model:

Type	Name
Dependent variable	• BAL PD Response
Fixed continuous independent variable	• Baseline*PD marker
Fixed categorical independent variables	• Treatment*PD marker

Information on the effects and prior distributions for parameters:

Type	Name (#Levels)	Parameters	Priors
Fixed Continuous	Baseline (2h) * PD marker (2)	#1 Baseline (2h) * Ind[Total Protein = 1]	N(Mean=0, Var=1E6)
		#2 Baseline (2h) * Ind[Neutrophil = 1]	N(Mean=0, Var=1E6)
Fixed Categorical	Treatment * PD marker (4)	#1 Placebo * Ind[Total Protein = 1]	N(Mean=0, Var=1E6)
		#2 Placebo * Ind[Neutrophil = 1]	N(Mean=0, Var=1E6)
		#3 GSK2798745 * Ind[Total Protein = 1]	N(Mean=0, Var=1E6)
		#4 GSK2798745 * Ind[Neutrophil = 1]	N(Mean=0, Var=1E6)
Random	Subjects	Separate value per subject, sampled as i.i.d. $\sim N(0, \sigma_{Subject}^2)$	$\sigma_{Subject}^2 \sim \text{Gamma}(0.001, 0.001)$

- The default prior for the VCV matrix would be an Inverse-Wishart with parameters **k** and **S** (where **S** = (k - p - 1) * **R** and p = dimension of the VCV matrix). Under this framework, **R** can be thought of as a best guess for the VCV of the endpoints/timepoints being modelled. Care should be taken in the choice of **k** and **R** for each endpoint to ensure it is uninformative.
- Separate variance-covariance matrices will be used for treatment groups if there is sufficient

information/data to allow for this (i.e. convergence occurs for all parameters and values do not get “stuck” at zero) to obtain separate estimates for the correlation between the endpoints. If there is not sufficient information then the default position is for treatment groups to share a common variance-covariance matrix.

- An optional exploration/model building step may take place by adding other covariates to the model that may explain a significant proportion of variance in the response and/or imbalance between treatment groups at baseline and/or be justified by biological rationale/expert judgment or statistical tools (raw plots and model selection criteria). Only the results of the final model would be reported in the Clinical Study Report (CSR).
- For the final model, appropriate combinations of model parameters should be combined to obtain treatment effects of interest, including performing any back-transformations that are required. For example, assuming \log_e transformation is required, the percentage change for GSK2798745 relative to placebo in 26h total protein will be obtained by computing $\exp(\beta_{GSK2798745, Total Protein} - \beta_{Placebo, Total Protein})$ for each MCMC iteration, which should be programmed between the BEGINNODATA and ENDNODATA statements (within PROC MCMC procedure).
- To obtain probability statements for parameters/effects of interest use binary flag variables. For each MCMC iteration if the condition is satisfied the iteration is flagged as a 1, if not it is flagged as 0. The proportion of iterations flagged as 1 gives the posterior probability of the statement of interest i.e. the proportion of MCMC iterations for which the percentage reduction in the BAL biomarker for GSK2798745 c.f. placebo for the specified sampling timepoint is greater than zero.
- For example, the SAS syntax for computing the flag for any percentage reduction in BAL total protein as well as neutrophils would be: $flagsuccess_TPROTNEU = (ratio_TPRO < 1 \text{ and } ratio_TNEU < 1);$. Where $ratio_TPRO$ is the parameter used to store the ratio of adjusted posterior medians for GSK2798745 relative to placebo for total protein, calculated as $\exp(\beta_{GSK2798745, Total Protein} - \beta_{Placebo, Total Protein})$ and $flagsuccess_TPROTNEU$ being the binary variable where any percentage reduction in both total protein and total neutrophil, active relative to placebo, flags success. This will be computed for a number of different effects of interest: 10%, 25% percentage reduction, etc

Model Checking & Diagnostics

- See Section 7.1.5.1 (Model Checking and Diagnostics)

Model Results Presentation

- Point estimates (median values of posterior distributions), the standard deviation of the posterior distribution (SDs) and 95% credible intervals (CrI) intervals will be presented for each treatment group and treatment comparison (absolute and percentage change) at each sampling time point. A number of posterior probability statements will also be expressed, as described in Table 2 of Section 7.2.5.1 (Model Results Presentation) for each timepoint.
- Point estimates for each treatment group and treatment comparison (absolute and percentage change) for each endpoint will be expressed graphically. See Appendix 11: List of Data Displays for example displays.
- The joint posterior probability statements of interests in Table 2 were correct at the time of writing but may not be limited to these listed.

Table 4 Posterior Probability Statements of Interest

Posterior Probability Statement (where X_{TP} = treatment ratio of GSK2798745 / Pbo for 26h total protein)	Interpretation
PP ($X_{TP} \leq 0.25$ and $X_{NE} \leq 0.25$)	Posterior probability of at least a 75% reduction in both mean BAL total protein and total neutrophil counts for GSK2798745 relative to placebo
PP ($X_{TP} \leq 0.5$ and $X_{NE} \leq 0.5$)	Posterior probability of at least a 50% reduction in both mean BAL total protein and total neutrophil counts for GSK2798745 relative to placebo
PP ($X_{TP} \leq 0.75$ and $X_{NE} \leq 0.75$)	Posterior probability of at least a 25% reduction in both mean BAL total protein and total neutrophil counts for GSK2798745 relative to placebo
PP ($X_{TP} \leq 0.9$ and $X_{NE} \leq 0.9$)	Posterior probability of at least a 10% reduction in both mean BAL total protein and total neutrophil counts for GSK2798745 relative to placebo
PP ($X_{TP} \leq 1$ and $X_{NE} \leq 1$)	Posterior probability of any reduction in both mean BAL total protein and total neutrophil counts for GSK2798745 relative to placebo
PP ($X_{TP} > 1$ and $X_{NE} > 1$)	Posterior probability of any increase in both mean BAL total protein and total neutrophil counts for GSK2798745 relative to placebo
PP ($X_{TP} > 1.1$ and $X_{NE} > 1.1$)	Posterior probability of at least a 10% increase in both mean BAL total protein and total neutrophil counts for GSK2798745 relative to placebo
PP ($X_{TP} > 1.25$ and $X_{NE} > 1.25$)	Posterior probability of at least a 25% increase in both mean BAL total protein and total neutrophil counts for GSK2798745 relative to placebo
PP ($X_{TP} > 1.5$ and $X_{NE} > 1.5$)	Posterior probability of at least a 50% increase in both mean BAL total protein and total neutrophil counts for GSK2798745 relative to placebo
PP ($X_{TP} > 1.75$ and $X_{NE} > 1.75$)	Posterior probability of at least a 75% increase in both mean BAL total protein and total neutrophil counts for GSK2798745 relative to placebo

- **PD_F2:** The correlation between endpoints for each treatment arm will be extracted from the statistical analysis and displayed on a panel scatter plot showing 26h total protein against 26h total neutrophils, with separate panels for treatment arm (as it is anticipated the relationship between endpoints will be different between treatment arms).

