Summary of Posterior Distributions and Posterior Probability Statements
for Primary Analysis of 26 h BAL Total Protein

Endpoint/Analyte	Comparison	Median	SD	95% CrI	75% CrI	MCSE/SD
26 h Total Protein	Absolute Difference (Active - Placebo)	xxxxx	xxxxx	(xxxxx, xxxxxx)	(xxxxx, xxxxx)	xxxx
	Percentage Reduction (Active cf. Placebo)	xxxxx	xxxxx	(xxxxx, xxxxxx)	(xxxxx, xxxxx)	xxxx

Example: PD_T2 (continued)
Protocol: 207464
Page x of x
Population: Evaluable

Data as of xx-xxx-xxxx

[figure not shown]
Table 2.3 (cont.)
Summary of Posterior Distributions and Posterior Probability Statements
for Primary Analysis of 26 h BAL Total Protein

Response	Comparison	Posterior Probability Statement	Value
26 h Total Protein	Median Percentage Change (Active cf. Placebo)	At least a 75% mean reduction (Active c.f. Placebo)	0.002
		At least a 50% mean reduction (Active c.f. Placebo)	0.221
		At least a 25% mean reduction (Active c.f. Placebo)	0.522
		At least a 10% mean reduction (Active c.f. Placebo)	0.721
		Any mean reduction (Active c.f. Placebo)	0.952
		Any mean increase (Active c.f. Placebo)	0.048
		At least a 10% mean increase (Active c.f. Placebo)	0.030
		At least a 25% mean increase (Active c.f. Placebo)	0.018
		At least a 50% mean increase (Active c.f. Placebo)	0.002
		At least a 75% mean increase (Active c.f. Placebo)	0.000

Example: PD_F1
Protocol: 207464
Population: Evaluable

Page 1 of n

Figure 2.10
Boxplots of Total Protein by Timepoint/Challenge and Treatment Group

[figure not shown]

Example: PD_F2
Protocol: 207464
Population: Evaluable

Page 1 of n

Figure 2.73
Scatter Plot of 26 Total Protein v 26h Total Neutrophil in the LPS Challenged Lobe

[figure not shown]
207464 Planning: Scatter plot of 26h Total Protein v 26h Total Neutrophil in the LPS Challenged Lobe

Note: correlation is rho value taken from unstructured variance-covariance matrix in multivariate analysis

[figure not shown]
Example: PD_F3
Protocol: 207464
Population: Evaluable

Figure 2.12
Participant Profiles of Baseline (2h), LPS lobe (26h) and Saline Lobe (26h) BAL Total Protein by Treatment Group

[figure not shown]
Example: PD_F4
Protocol: 207464
Population: Evaluable

Table 2.13
Total Protein Point Estimates and 95% Highest Posterior Density Intervals from the Primary Analysis

Example: PD_F5
Protocol: 207464
Population: Evaluable

[figure not shown]
Figure 2.14
Total Protein Posterior Density Plots from the Primary Analysis

Example: PD_F6
Protocol: 207464
Population: All Subjects

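### In the optional protein–neutrophil model, the correlation to be plotted is not identified, because a random subject effect is added on top of an unstructured covariance matrix

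*SAP*

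**What the plan says.** SAP 7.3.5.3 describes an optional exploratory model with one stated aim: "This analysis may be conducted to better understand the correlation between the endpoints".

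Its covariance side has two parts:

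- The table of effects and priors has a random row for subjects, "Separate value per subject, sampled as i.i.d" normal with mean zero. Its variance has a Gamma(0.001, 0.001) prior. The section does not say whether the second number is a scale or a rate.
- Below the table: "The default prior for the VCV matrix would be an Inverse-Wishart with parameters" k and S, where S = (k − p − 1)·R and R is a prior guess at the matrix. Neither k nor R is given. Matrices are fitted separately by arm if the data allow, otherwise in common.

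On the reported quantity, the note for PD_F2 says "The correlation between endpoints for each treatment arm will be extracted from the statistical analysis". The mock shell in Appendix 12 is specific about its source: "Note: correlation is rho value taken from unstructured variance-covariance matrix in multivariate analysis".

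On the data, the figure is described as "showing 26h total protein against 26h total neutrophils", which is one value of each per participant. The 2 h value enters only as a covariate, "Baseline*PD marker".

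The blood-biomarker model in SAP 7.3.5.1 uses the same VCV wording and has no random subject row.

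**The concern.** A shared subject intercept and an unstructured matrix both account for the covariance between a participant's two outcomes. With repeated values of each endpoint the data could separate them. With a single value of each they cannot, and any covariance moved into the subject effect disappears from the VCV without changing the fit.

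The figure takes its correlation from the VCV only. That number therefore leaves out whatever the subject effect has absorbed, and the priors determine how much that is. The quantity at risk is the one the analysis is meant to deliver.

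**Working it through.** The plan states no power, sample size or numerical correlation for this model, so there is no figure to reproduce. The check is of identification.

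**Notation.** V is the total covariance of the two log outcomes, with variances v1 and v2 and covariance c. The VCV has elements r11, r22 and r12. The subject variance is s.

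**Parameter count.** The model implies v1 = r11 + s, v2 = r22 + s, c = r12 + s.

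- Common VCV: 4 parameters (r11, r22, r12, s), 3 moments; the map has rank 3.
- Separate VCVs with one s: 3 + 3 + 1 = 7 parameters, 6 moments; rank 6.

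One direction is unidentified in both cases, so falling back to a common matrix does not help.

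**Correlation along the flat direction.** For fixed V,

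`rho_VCV = (c − s) / sqrt((v1 − s)(v2 − s))`

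for s from 0 up to `(v1·v2 − c²) / (v1 + v2 − 2c)`, where the VCV stops being positive definite.

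**Inputs.** v1 = 0.25 is the log-scale variance of post-LPS protein in protocol 10.1 (95% CI 0.13 to 0.69; not a residual variance after baseline adjustment). Assumed, because the documents give no figure: v2 = 0.64 and total correlation 0.50. Then c = 0.50 × sqrt(0.25 × 0.64) = 0.20, and the limit on s is (0.16 − 0.04)/(0.89 − 0.40) = 0.12/0.49 ≈ 0.245.

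| s | rho_VCV |
|---|---|
| 0 | 0.50 |
| 0.05 | 0.15/sqrt(0.20 × 0.59) = 0.44 |
| 0.10 | 0.10/sqrt(0.15 × 0.54) = 0.35 |
| 0.15 | 0.05/sqrt(0.10 × 0.49) = 0.23 |
| 0.20 | 0.00 |
| 0.24 | −0.04/sqrt(0.01 × 0.40) = −0.63 |

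V is the same in every row, so the likelihood is too. In a simulated set of 60 participants with v2 = 0.50, the log-likelihood was −82.2438 at every point while rho_VCV went from 0.50 to −0.35.

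**Range over the assumptions** (v1 = 0.25; s at half and at 90% of its limit):

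| v2 | Total correlation | rho_VCV, half | rho_VCV, 90% |
|---|---|---|---|
| 0.25 | 0.3 | −0.04 | −0.69 |
| 0.25 | 0.5 | 0.20 | −0.54 |
| 0.25 | 0.7 | 0.48 | −0.28 |
| 0.50 | 0.3 | 0.00 | −0.62 |
| 0.50 | 0.5 | 0.26 | −0.35 |
| 0.50 | 0.7 | 0.57 | 0.27 |
| 1.0 | 0.3 | 0.09 | −0.40 |
| 1.0 | 0.5 | 0.38 | 0.18 |
| 1.0 | 0.7 | 0.68 | 0.78 |

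The shift is usually downward but not always; the last row moves towards +1.

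**What the priors do.** The posterior of rho_VCV was found by numerical integration, assuming 60 participants, a common VCV, v1 = 0.25, v2 = 0.64, total correlation 0.50 and k = 4 or 5.

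- Gamma read as a rate, R = diag(0.25, 0.64): median about 0.49 (95% interval about 0.23 to 0.67 at k = 4).
- Gamma read as a rate, R half that size or 0.1 times the identity: median still 0.48 to 0.49, but the lower 95% limit falls below zero, to about −0.7 at worst.
- Gamma read as a rate, R = 0.01 times the identity: median about −0.8 to −0.9.
- Gamma read as a scale: s is forced to about zero, and the median is 0.46 to 0.51 for every R tried, from 0.01 times the identity to the identity.

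The total correlation stays between about 0.45 and 0.53 throughout.

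**The case against.** The best defence is that the SAP's priors are proper, so rho_VCV has a posterior, and the stated Gamma prior puts almost all its mass near zero. With R set to a sensible guess at the matrix, the reported value is close to the total correlation. The value of R that turns the sign is far from such a guess. The only place where the SAP names the second parameter of this Gamma is section 3.1, for standard deviations, where it is a scale; read that way here, the problem almost vanishes. This stands as a limit on size. A reader might infer that the printed correlation would be arbitrary, and the documents do not support that: the result is prior-sensitive, and some choices return nearly the right answer. The defect remains, because k, R and the Gamma parameterisation are left open and nothing in the data would correct a poor choice.

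The random row may also be a template leftover. It is missing from the list of terms to be fitted, the section still carries text about blood biomarkers, and the figure footnote mentions only the unstructured matrix. That is plausible, but the list of terms also omits the intercept in other models, so it does not settle the matter. If it is a leftover, the remedy is the same.

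A reader might go further and infer that the whole model fails. It does not. Only the split between s and the VCV is unidentified; the fixed effects, the treatment ratios and the Table 4 joint probabilities depend on the total covariance, which is identified.

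Poor mixing is likely but has not been shown. The checks in SAP 7.1.5.1 (trace plots, at least two chains, Monte Carlo error, autocorrelation) could reveal it but cannot restore identification.

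**Conclusion.** The point holds for the covariance part of this one optional model. As written, the VCV correlation that PD_F2 displays is not identified. It can equal the total correlation or differ from it greatly, even in sign, depending on priors that the SAP leaves partly open. In the example, 0.50 and −0.63 have equal likelihood.

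The parameter count needs only one 26 h value per endpoint per participant and both terms being fitted together. The sizes rest on the assumed neutrophil variance, total correlation, k and R, and on an unadjusted protein variance.

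The consequence is contained. The analysis may not be run, its table and listing are conditional outputs, and its displays belong to the final analysis only. It informs no interim, success or data-review decision and does not touch the primary endpoint. It is still worth correcting, because the affected number is the purpose of the analysis.

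**What to change.** In SAP 7.3.5.3, delete the random subject row and its Gamma(0.001, 0.001) prior. Keep the unstructured VCV as the only within-subject term, as in 7.3.5.1, and report rho from it. The count becomes 3 parameters for 3 moments (6 for 6 by arm), and the VCV correlation equals the total correlation. With 60 participants and an observed correlation of 0.50, the posterior median is about 0.49 (95% interval about 0.28 to 0.66).

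If the random row is kept, change the PD_F2 note and footnote so that the figure reports the correlation from the total covariance, `(r12 + s) / sqrt((r11 + s)(r22 + s))`, which is identified.

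The first option costs one deleted table row and makes the code simpler; the second changes one derived quantity and a footnote. Neither needs new data.

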8. SAFETY ANALYSES

The safety analyses will be based on the All Subjects population, unless otherwise specified.

8.1. Adverse Events Analyses

Adverse events analyses including the analysis of adverse events (AEs), Serious (SAEs) and other significant AEs will be based on GSK Core Data Standards. The details of the planned displays are provided in [Appendix 11: List of Data Displays](#).

8.2. Clinical Laboratory Analyses

Laboratory evaluations including the analyses of Chemistry laboratory tests, Hematology laboratory tests, Urinalysis, and liver function tests will be based on GSK Core Data Standards. The details of the planned displays are in [Appendix 11: List of Data Displays](#).

8.3. Other Safety Analyses

The analyses of non-laboratory safety test results including ECGs and vital signs will be based on GSK Core Data Standards, unless otherwise specified.

The CSSRS questionnaire will be summarised using a listing and summary table. FOBT results will summarised using a listing and summary table.

The details of the planned displays are presented in [Appendix 11: List of Data Displays](#)

9. PHARMACOKINETIC ANALYSES

9.1. Primary Pharmacokinetic Analyses

9.1.1. Endpoint / Variables

9.1.1.1. Drug Concentration Measures

Refer to [Appendix 5: Data Display Standards & Handling Conventions \(Section 12.5.3 Reporting Standards for Pharmacokinetic\)](#)

9.1.1.2. Derived Pharmacokinetic Parameters

Pharmacokinetic parameters will be calculated by standard non-compartmental analysis according to current working practices and using the currently supported version of WinNonlin. All calculations of non-compartmental parameters will be based on actual sampling times. Pharmacokinetic parameters listed will be determined from the plasma concentration-time data, as data permits.

Parameter	Parameter Description
C _{max}	Plasma GSK2798745 for Day 1
T _{max}	Plasma GSK2798745 for Day 1
AUC(0-26)	Plasma GSK2798745 for Day 1 & Day 2

NOTES:

- Additional parameters may be included as required.

9.1.2. Population of Interest

The primary pharmacokinetic analyses will be based on the pharmacokinetic population, unless otherwise specified.

9.1.3. Statistical Analyses / Methods

Details of the planned displays are provided in [Appendix 11: List of Data Displays](#) and will be based on GSK Data Standards and statistical principles.

Unless otherwise specified, endpoints / variables defined in Section 9.1.1 will be summarised using descriptive statistics, graphically presented (where appropriate) and listed.

9.2. Secondary Pharmacokinetic Analyses

9.2.1. Endpoint / Variables

9.2.1.1. Drug Concentration Measures

Refer to [Appendix 5: Data Display Standards & Handling Conventions \(Section 12.5.3 Reporting Standards for Pharmacokinetic\)](#)

9.2.1.2. Derived Pharmacokinetic Parameters

Pharmacokinetic parameters will be calculated by standard non-compartmental analysis according to current working practices and using the currently supported version of WinNonlin. All calculations of non-compartmental parameters will be based on actual sampling times. Pharmacokinetic parameters listed will be determined from the plasma concentration-time data, as data permits.

Parameter	Parameter Description
Cmax	Plasma metabolite GSK3526876 Day 1
Tmax	Plasma metabolite GSK3526876 Day 1
AUC(0-26)	Plasma metabolite GSK3526876 Day 1 & 2
BAL 2h	BAL metabolite GSK3526876 Day 1
BAL 26h	BAL metabolite GSK3526876 Day 1
BAL 2h	BAL GSK2798745 concentration at 2h
BAL 26h	BAL GSK2798745 concentration at 26h

NOTES:

- Additional parameters may be included as required.

9.2.2. Population of Interest

The secondary pharmacokinetic analyses will be based on the pharmacokinetic population, unless otherwise specified.

10. PHARMACOKINETIC / PHARMACODYNAMIC ANALYSES

The primary goal of this analysis is to characterize the pharmacokinetic / pharmacodynamic relationship of GSK2798745 administered orally in the participants.

10.1. Statistical Analyses / Methods

A summary of the planned pharmacokinetic / pharmacodynamic analyses are outlined below:

- Individual plasma GSK2798745 C_{max}, will be plotted against corresponding BAL 2h GSK2798745 drug levels. Analysis may be undertaken to assess relationship of drug levels in plasma and target site (BAL).
- Individual plasma GSK2798745 AUC(0-26) and C₂₆ data will be plotted against BAL 26h GSK2798745 drug levels. Regression analysis will be undertaken to assess relationship of drug levels in plasma and target site (BAL)
- Individual plasma GSK2798745 AUC(0-26), C₂₆ and C_{max} data will be plotted against total BAL protein at 26h (primary clinical endpoint). Placebo treatment data (i.e. 0 drug concentration and corresponding total BAL protein will also be included in the PK-PD analysis. Analysis may be undertaken to evaluate the association between GSK2798745 PK parameters and change in BAL total protein.

Data specifications for PK/PD analyses presented in [Appendix 11: Pharmacokinetic / Pharmacodynamic Analyses](#).

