- *Timing of challenge:* Baseline BAL sampling prior to administration of study drug is not considered feasible due to the burden of bronchoscopy (i.e. two procedures required – one pre and one post dose to instil LPS). A baseline bronchoscopy is planned 2 h after administration of the first dose, with the aim of maximising exposure to GSK2798745 (in healthy volunteers, the median [range] Time to reach maximum plasma concentration (Tmax) of the tablet formulation of GSK2798745 to be used in this study is 1.5 h [1–3 h]). Drug on board at the time of baseline BAL fluid sampling is expected to have little to no effect on baseline BAL total protein concentrations as TRPV4 channels are quiescent until stimulated and blockade of these channels does not affect barrier permeability of ‘healthy’ endothelial cells [internal data]. The effects of LPS to induce endothelial permeability are believed to occur rapidly. Investigation of LPS induced permeability and markers of cell activation and inflammation over time consistently indicates that the initial events leading to increased barrier permeability and inflammation occur within first 2 h post intratracheal (i.t.) LPS exposure; where any earlier measurements are limited. LPS induces intracellular stress fibre formation within 5 min in both human dermal microvascular endothelial cells (HMVEC) endothelial and A549 epithelial cells [Ngamsri, 2010]. Increased levels of TNF $\alpha$  following i.t. LPS instillation are observed within 2 h in man [O’Grady, 2001] and other pro-inflammatory mediators within 4 h in a mouse model of acute lung injury (ALI) [Bosmann, 2012]. Permeability across an endothelial monolayer is observed after 0.5 h and peaks at 2 h post-LPS [Bannerman, 1998]. BAL total protein increases following LPS i.t. challenge in man as early as 2 h and reaches significance at 6 h post-LPS [Matthay, 2012] with significant increases in neutrophil counts also observed as early as 2 h. Looking to a systemic LPS model of sepsis with a higher LPS insult, earlier sampling is possible and high levels of inflammatory mediators are measured within 1 h, which reach plateau by 3 h. Therefore, despite our conservative treatment effect prediction (see Section 5.5), we expect that high plasma and/or alveolar fluid concentrations of GSK2798745 will be required at the time of and/or soon after the challenge, in order to inhibit the effects of LPS. Therefore, LPS will be administered shortly after time of Tmax (1.5-hours) to ensure sufficient drug on board.

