### 7.1. Treatments Administered

Study Treatment Name:	GSK2798745	Matching Placebo	Challenge Agent: GMP grade lipopolysaccharide from Escherichia coli (E. Coli Group 0113:H10:K Negative) for the segmental LPS challenge
Dosage formulation:	White to slightly coloured, round biconvex tablet. Product: AP, Tab-A	White to slightly coloured, round biconvex tablet. Product code: CET, Tab-A..	LPS is available from stock lyophilized in a 1 microgram vial, formulated in 1% lactose and 0.1% PEG6000. Clear solution.
Unit dose strength(s)/Dosage level(s):	Unit dose strength 2.4 mg. Dosage Levels: 4.8 mg and 2.4 mg	Not applicable	4 ng/kg
Route of Administration	Oral	Oral	Direct application to the lung segment, via bronchoscopy
Dosing instructions:	Two tablets to be taken on the morning of Day 1, then one tablet to be taken 12 hours later.	Two tablets to be taken on the morning of Day 1, then one tablet to be taken 12 hours later.	One single instillation of 10 mL by bronchoscopy 2 hours after dosing with GSK2798745 or placebo on Day 1.

Study Treatment Name:	GSK2798745	Matching Placebo	Challenge Agent: GMP grade lipopolysaccharide from Escherichia coli (E. Coli Group 0113:H10:K Negative) for the segmental LPS challenge
Packaging and Labeling	GSK2798745 tablets will be provided in high-density polyethylene (HDPE) bottles with child-resistant closures that include induction-seal liners. Each bottle will be labelled as required per country requirement.	Placebo tablets will be provided in high-density polyethylene (HDPE) bottles with child-resistant closures that include induction-seal liners. Each bottle will be labelled as required per country requirement.	-
Manufacturer	GSK	GSK	List Laboratories, Inc.

Sterile saline (0.9%) for control challenge will be sourced by the clinical site.

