11. Blood samples for exploratory biomarkers. The 2- and 26-h blood samples should be taken immediately before BAL sampling.
12. PK samples will be taken pre-dose and at 0.5, 1, 1.5, 2, 2.5, 3, 6, 8, 12, 12.5, 13, 13.5, 14, 15, 24 and 26 h after the first dose. The 2- and 26-h blood sample should be taken immediately before BAL sampling

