12.9. Appendix 9: Pharmacokinetic / Pharmacodynamic Analyses

12.9.1. Pharmacokinetic / Pharmacodynamic Dataset Specification

Specification for PK-PD dataset [Proposed dataset name PKPD]

Variable short name	Assessment description	Format	Unit	Valid Values / Format
C	Data Identifier	Integer	-	0
ID	Unique subject number	Numeric		Different ID for different subject
STUD	Protocol Number	Integer	-	207464
SUBJ	Subject identifier in study	Integer	-	Maximum 10 characters (numeric or text). Different identifier for each subject
CENT	Study centre identifier	Integer	-	
DAY	Day of sampling	Integer	See footnotes	See footnotes
C2	Conc of GSK2798745 2 h post first dose	Decimal 3 d.p	ng/mL	Numeric – For placebo TRT arm C2 = 0
C26	Conc of GSK2798745 26 h post first dose	Decimal 3 d.p	ng/mL	Numeric - For placebo TRT arm C26 = 0
AUC26	Area under curve (0-26h)	Decimal 3 d.p	ng.h/mL	Numeric - For placebo TRT arm AUC26 = 0
Analyte	Drug analysed	Integer	-	GSK2798745
Base_PD	Baseline corrected BAL total protein (i.e. before LPS challenge and 2h post dose)	Decimal 3 d.p	-	BAL total protein
745_PD	Corrected BAL total protein at 26h post dosing with GSK2798745 (i.e. 24h post LPS challenge)	Decimal 3 d.p		BAL total protein
AGE	Age	Decimal	Yrs	Integer. Age in years at time of screening rounded down to give age at last birthday.
WT	Weight	Decimal	Kg	Weight in kilograms at time of screening.
BMI	Body mass index	Decimal	kg/m ²	Body mass index calculated as weight divided by height squared
SEX	Subject gender	Integer	-	Integer. One of the following - 1 = Male

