12.11.10. Pharmacokinetic / Pharmacodynamic Figures

Pharmacokinetic / Pharmacodynamic: Figures					
No.	Population	IDSL / Example Shell	Title	Programming Notes	Deliverable [Priority]
PK / PD					
7.1.	Evaluable	PKPD_F1	Scatter Plots of Plasma PK Parameters (AUC_{0-26} , C_{26} , C_{max}) v 26h BAL Total Protein.	Page 1: Plasma AUC_{0-26} v 26h BAL Total Protein Page 2: Plasma C_{26} v 26h BAL Total Protein Page 3: Plasma C_{MAX} v 26h BAL Total Protein	SAC [1]
7.2.	Evaluable	PKPD_F1	Plots of BAL GSK2798745 Concentrations v 26h BAL Total Protein	Page 1: BAL C_2 v 26h BAL Total Protein Page 2: BAL C_{26} v 26h BAL Total Protein	SAC [1]

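### The PK/PD plan pairs the 2 h BAL drug level with a Day 1 plasma Cmax that can occur after that BAL, while the plasma sample drawn just before it is in no plasma-BAL or PK/PD scatter plot.

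*SAP*

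**What the plan says.** - **Dosing (Protocol 7.1).** "Two tablets to be taken on the morning of Day 1, then one tablet to be taken 12 hours later". The schedule in SAP 12.2.3 places both doses, 0 h and 12 h, under Day 1.
- **Sampling (SAP 12.2.3, footnote 12).** "PK samples will be taken pre-dose and at 0.5, 1, 1.5, 2, 2.5, 3, 6, 8, 12, 12.5, 13, 13.5, 14, 15", then 24 and 26 h. The same footnote adds: "The 2- and 26-h blood sample should be taken immediately before BAL sampling". LPS follows the baseline BAL, close to 2 h.
- **Cmax and Tmax (SAP 9.1.1.2).** Each is described only as "Plasma GSK2798745 for Day 1". No dosing interval is given.
- **Plasma against BAL drug (SAP 10.1; Figures 4.9 and 4.10).** Plasma Cmax "will be plotted against corresponding BAL 2h GSK2798745 drug levels". For the 26 h BAL level, the plasma partners are AUC(0-26) and C26.
- **Plasma against response (SAP 10.1; Figure 7.1).** AUC(0-26), C26 and Cmax are plotted against 26 h BAL total protein; the Cmax page reads "Page 3: Plasma C_{MAX} v 26h BAL Total Protein".
- **PK/PD dataset (SAP 12.9.1).** It includes C2, described as "Conc of GSK2798745 2 h post first dose", without saying whether this is plasma or BAL.
- **Rationale (Protocol 5.4).** High concentrations of "GSK2798745 will be required at the time of and/or soon after the challenge, in order to inhibit the effects of LPS". The tablet's Tmax is given as median 1.5 h, range 1-3 h.

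**The concern.** A drug level in BAL fluid taken at 2 h cannot depend on a plasma peak reached later. As defined, Cmax is the highest Day 1 value over two doses. For some participants it will come from the 2.5 h or 3 h sample, and for a few it could come from 12.5-15 h. Those points pair a 2 h lung level with a later plasma level, which blurs the plasma-to-lung relation that the plot is meant to show. A Tmax pooled over both doses would likewise mix values near 1.5 h with any near 13-14 h.

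The matched plasma value exists, and the plan applies the matching principle at 26 h. It gives no reason for treating 2 h differently. The comparison of plasma PK with the permeability effect, an exploratory objective in Protocol section 4, has a related gap: none of the three plasma measures in Figure 7.1 is defined at the time of challenge.

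**Working it through.** **1. Which plasma measure meets which BAL measure**

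| BAL measure | Plasma measure plotted | Same time? |
|---|---|---|
| Drug at 2 h (Figures 4.9/4.10, page 1) | Cmax, Day 1 | Not necessarily |
| Drug at 26 h (page 2) | AUC(0-26) | Covers 0-26 h |
| Drug at 26 h (page 3) | C26 | Yes |
| Protein at 26 h (Figure 7.1) | AUC(0-26), C26, Cmax | C26 only |

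The C2 in Figures 4.9, 4.10 and 7.2 is the BAL concentration. Plasma at 2 h appears only within the concentration-time displays (Table 4.1, Figures 4.1-4.3).

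**2. Typical profile.** The plan states no figure for this mismatch, so there is none to reproduce. Inputs: Tmax 1.5 h (Protocol 5.4); median Cmax 23.1 ng/mL and AUC0-24 272.4 ng.h/mL (Protocol Table 1); the second dose is half the first.

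One-compartment superposition: C(t) = S[g(t) + 0.5 g(t-12)], where g(t) = exp(-kt) - exp(-ka t) for t ≥ 0 and 0 otherwise.

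Matching the three inputs gives k = 0.1442/h (half-life 4.8 h), ka = 1.843/h and S = 31.12. Check: ln(1.843/0.1442)/(1.843 - 0.1442) = 1.50 h.

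- First peak: 31.12 × (0.8055 - 0.0630) = 23.1.
- C2: 31.12 × (0.7495 - 0.0251) = 22.5, so C2/first peak = 0.976.
- Second peak: 16.05 at 13.3 h, so second/first = 0.695.
- C26: 2.8 ng/mL.

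**3. A profile that also meets the 26 h prediction.** Protocol 5.5.1 gives 71.1% inhibition at 26 h and an IC50 of 2.1-3.2 ng/mL. Assuming a simple Emax model (Emax 1, Hill 1), C26 = IC50 × 0.711/0.289 = 5.2 to 7.9 ng/mL, above the 2.8 in step 2. Biexponential fits to Tmax, Cmax, AUC0-24 and a C26 of 5.2, 6.5 or 7.9 give second/first peak 0.72-0.77 and C2/first peak 0.95-0.97. At 7.9, two of the three fits are only approximate.

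**4. Ends of the stated Tmax range** (half-life 4.8 h). C2/first peak is 0.90 at Tmax 1 h and 0.94 at Tmax 3 h.

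**5. What would make the second peak the larger** (one compartment, Tmax 1.5 h, AUC0-24 272.4):

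| Half-life | Second/first peak | C2/first peak | Overall Cmax (ng/mL) |
|---|---|---|---|
| 8 h | 0.87 | 0.98 | 17.5 |
| 10 h | 0.95 | 0.99 | 15.7 |
| 12 h | 1.02 | 0.99 | 14.8 |
| 14 h | 1.07 | 0.99 | 14.7 |

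The stated median Cmax is 23.1, with 95% prediction interval 15.2-34.4. At 12-14 h the typical Cmax is below the lower limit of that interval.

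**6. Between-participant spread.** Profiles based on step 2 were simulated on the planned sampling grid. Assumed: variation of 0.20-0.25 on clearance and volume (the stated Cmax interval implies a log SD of ln(34.4/15.2)/(2 × 1.96) = 0.21), 0.3-0.7 on ka, and residual error 0-15%.

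- Observed Cmax after the 2 h BAL/LPS: 4-32% (of 30 active participants, 0.04 × 30 to 0.32 × 30, or about 1 to 10), mostly at 2.5-3 h.
- Observed Cmax after the second dose: 0.2-4.5% (about 0 to 1 of 30).
- Correlation of log Cmax with log C2: 0.75-0.98. The low end needs 15% residual error, which C2 carries as well.

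**The case against.** The best defence is that Cmax and C2 are nearly the same quantity for most participants, that the work is exploratory, and that the note to SAP 9.1.1.2 allows further parameters. The first two parts stand and limit the size of the point. The third is permission, not a plan.

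Four stronger readings are tempting, and the documents do not support them.

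- **Half or more of active participants could have their Cmax after the second dose.** That needs half-lives of about 12 h or more, for which the typical Cmax contradicts Protocol Table 1 (step 5).
- **A negative trial could not tell low exposure at challenge from a failed mechanism.** Figure 7.2 plots BAL drug at 2 h against 26 h protein, Table 4.3 and Figure 4.7 report BAL drug at 2 h, and the concentration-time displays include plasma at 2 h.
- **Cmax is the wrong measure against protein.** Protocol 5.4 also counts exposure soon after the challenge, which a 2.5-3 h peak satisfies. A plasma C2 page is a useful addition there, not a correction.
- **The PK/PD dataset omits Cmax.** The table in SAP 12.9.1 breaks off in the available text, so this cannot be asserted.

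**Conclusion.** The point holds for the 2 h pairing. An undivided Day 1 Cmax is set against a BAL level that may precede it, and the matched plasma value is left out of the plasma-BAL and PK/PD scatter plots. That Cmax spans both doses is inferred: it is labelled Day 1, both doses fall on Day 1, and nothing limits it to the first.

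The effect is modest. Typical C2 is about 0.95-0.99 of the first-dose peak. The usual mismatch would be a first-dose peak at 2.5-3 h; a second-dose Cmax should be uncommon. The 4-32% and 0.2-4.5% ranges rest on assumed variability and on a base profile that meets the stated Cmax and AUC0-24 but not the 26 h inhibition. The biexponential profiles, with a slightly higher second peak, were not simulated. The primary analysis, interim rules and success criterion are unaffected.

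**What to change.** 1. In SAP 10.1 and on page 1 of Figures 4.9 and 4.10, plot plasma C2 against BAL 2 h, in place of Cmax or beside it.
2. Add a page to Figure 7.1 for plasma C2 against 26 h BAL total protein.
3. In SAP 9.1.1.2, derive Cmax and Tmax separately for 0-12 h and 12-26 h, counting the second Tmax from the second dose. Keep the overall Cmax for comparison with the 50 ng/mL limit in Protocol 5.5.1. The metabolite entries in SAP 9.2.1.2 use the same Day 1 label and can follow the same rule.
4. In SAP 12.9.1, state that C2 is the plasma concentration.

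The cost is SAP wording, a few derived variables and two plot pages. No new samples or assays are needed.
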